#### Attachments

Attach Type	File Name
ResearchProcedures	07_release_form.doc

#### Data Collection & Research Materials

In this section, please provide the following:

- Describe all sources or methods for obtaining research materials about or from living individuals (such as specimens, records, surveys, interviews, participant observation, etc.), and explain why this information is needed to conduct the study.
- For each source or method described, please list or attach all data to be collected (such as genetic information, interview scripts, survey tools, data collection forms for existing data, etc.).
- If you will conduct a record or chart review, list the beginning and end dates of the records you will view.

Neuroimaging data will be acquired on a Siemens 3-Tesla (3T) PRISMA scanner. A high-resolution (1 cubic millimeter voxels) T1-weighted MP-RAGE structural image will be acquired for each subject. Functional images will be acquired using echo-planar imaging. Hyper-angulated volumes will be acquired with 37 ascending and interleaved slices at an angle 30-degrees to the anterior-posterior commissure to prevent OFC washout. Additional parameters will be similar to those used in other approved neuroimaging protocols in our lab (e.g., a repetition time (TR) of 2 seconds, echo time (TE) of 25 ms, a flip angle of 90 degrees, and functional voxels of size 3.4mm x 3.4mm x 4.0mm). Image preprocessing will be performed in statistical parametric mapping (SPM) 12 software using standard procedures (see Wesley et al., 2014). Data from functional scans will be treated similarly to fMRI data in previous studies (e.g., slice-timing corrected, head-motion corrected, warped into MNI standard space, re-sliced to 4 cubic millimeter voxels and smoothed with an 8mm full-width, half-maximum (FWHM) Gaussian kernel).

**Experimental Session Outcomes:** Physiological outcomes will include measurements of heart rate and blood pressure collected at hourly intervals throughout the session before each block of experimental tasks. Performance will be measured on 4 experimental tasks at baseline (approximately 30 minutes after arrival; 1 hour before THC administration) and immediately following TMS (approximately 4.5 hours after arrival; 3 hours after THC administration) (Figure 1).

Task 1: The visual analog scale (VAS) task consists of 24 items used previously to assess the subjective effects of THC (cf. Lile et al., 2015). Briefly, it measures positive (e.g., like drug), negative (e.g., nauseated) and cannabis-specific (e.g., high) subjective outcomes. Items are presented individually and measured by marking a 100-unit line anchored on the extremes by "Not At All" and "Extremely".

Task 2: A Probabilistic Reinforcement-Learning Choice (PRLC) task (cf. Rutledge et al., 2009). During this task, subjects complete two types of trials, control trials and choice trials. Control trials are inserted at the beginning and end of the task, in which subjects will be instructed to select a randomly scheduled option and will be provided feedback that is visually similar to that in choice trials. Control trials will permit neural activity related to decision-making to be isolated from activity associated with performing the task (e.g., visual, motor). During choice trials, subjects choose one of two options, signaled by visual cues (e.g., blue and green boxes). When reinforcement is scheduled for the chosen option, subjects are notified that they have earned money (e.g., \$1.00); or are informed that they did not earn money. Four probability ratios for the two options are used (e.g., 6:1, 2:1, 1:2, and 1:6). Trials are divided into un-signaled blocks, in which the identity of the higher reward probability option is reversed. Once a reinforcer is scheduled for an option, it remains available until that option is chosen, so that the longer an option remains un-chosen, the greater the probability that a reinforcer will be delivered by choosing it. Subjects will complete the task using an MRI-compatible keypad and visual display during the training session. During experimental sessions (Visits 2-7), subjects will complete the PRLC task on a laptop computer outside of the MRI scanner (no scanning occurs during experimental sessions). The PRLC task will end when a maximum number of reinforcers (e.g., 50) associated with one of the two options have been delivered, a fixed number of trials (e.g., 480) have been completed, or after exceeding a predetermined time limit (e.g., 45 minutes), whichever occurs first.

Task 3: The N-Back (N-Back) task is a validated working memory task (Jaeggi et al., 2010). Subjects are presented with a sequence of letters and must indicate when the letter currently being viewed matches the one from N steps earlier in the sequence. The load factor "N" is adjusted to make the task more or less difficult. Adjusted accuracy and reaction times on rounds of, 0-, 1-, 2-, and 3-Back are the primary outcomes.

Task 4: The Cannabis Purchasing Task (CPT) is an adaptation of an established hypothetical alcohol purchasing task (Amlung et al., 2015). Subjects are asked how many puffs of their preferred cannabis they would consume at 21 prices, ranging from free to \$20/unit. Primary outcomes of this task include elasticity of demand (a or "alpha") and intensity of demand ( $Q(0)$  or "Q naught"). These values are derived using nonlinear regression with the exponential demand equation (Hersh & Silberberg, 2008):  $\log(10)Q = \log(10)(Q(0)) + k(e^{-a*Q(0)*C}) - 1$ , where  $Q$  = consumption at a price;  $Q(0)$  = derived intensity of demand (consumption at zero price);  $k$  = a constant that denotes the range of consumption values in  $\log(10)$  units;  $C$  = the price of the commodity; and  $a$  = derived essential value (a measure of elasticity of demand). Greater values of  $Q(0)$  indicate greater consumption at unconstrained price (i.e., a theoretical price of zero). Greater values of  $a$  indicate a higher elasticity of demand or change in consumption with change in unit price.

**Behavioral Data Analyses:** Analysis of variance (ANOVA) will be used to compare group demographic data, data from primary outcome measures (above), and the primary molar PRLC task outcome, amount of money earned on the task. Data from the cannabis purchasing task (CPT) will be analyzed using the exponential demand equation (Hersh & Silberberg, 2008) described above. Molecular PRLC results will be analyzed using RL modeling of trial-by-trial data (Sutton & Barto, 1998), which uses the history of reinforcement for each choice, expressed as an expected value, to predict future choices. The value of the chosen option (option A) is updated via the outcome of the trial according to Equation 1 (see Figures attachment), where the updated value of option A is

determined by its current value and delta, the reward prediction error, defined in Equation 2 as the difference between the obtained or omitted reinforcer minus the outcome expectation that is determined by the reinforcement history for that option. The learning rate parameter (alpha) then determines the magnitude of expected value updating for option A. Finally, the probability of choosing A is determined via a softmax decision rule according to Equation 3, where the probability of choosing option A is a function of the difference between the values for A and B, multiplied by beta, a “temperature” parameter that alters the likelihood of the differential values between the alternatives dictating the predicted choice. Finally, A and B choices from the previous trial ( $C[a](t-1)$  and  $C[b](t-1)$ ) are multiplied by a perseveration parameter (“c”, the propensity of the individual to make the same choice on the current trial, regardless of reinforcement history). The free parameters alpha, beta, and c will be estimated using maximum likelihood estimation and differences (delta) in model fits estimated using Akaike’s Information Criterion (AIC) and pseudo r-squared, with parameters compared by model comparison and linear mixed modeling (Burnham & Anderson, 2002; Gelman & Hill 2006; McFadden 1974). Importantly, the RL modeling framework is flexible, and further decision-making complexities (e.g., outcome-specific learning rates or differential future-reward discounting) can be included when warranted. The alpha level will be set at the  $p<0.05$  for all analyses.

**Neuroimaging Data Analyses:** Brain activity and functional connectivity patterns will be associated with PRLC task outcomes and cannabis use demographics. For traditional analyses, separate first-level fixed-effects general linear models (GLMs) will be performed for each subject using SPM12 (Friston et al., 2007; Wesley et al., 2016). For molar analyses, blood-oxygen-level dependent (BOLD) signals associated with each condition of interest (selection and feedback event times for each choice alternative and control trials) will be convolved with the hemodynamic response function (HRF) and contrasted (choice events > control) to produce activity maps of each choice of interest. For molecular analyses, trial-by-trial RL modeling parameters (learning rate  $\alpha$  and reward prediction error  $\delta$ , and the perseveration parameter “ $c$ ”) will be parametrically regressed against the observed BOLD signal for events of interest (choice and feedback times for each choice option). Similarly, connectivity analyses will be performed using the psychophysiological interaction (PPI) method for both molar and molecular analyses (see Figure 2). In this case, first-level GLMs will contain interaction terms generated from primary eigenvariate timecourses extracted from corticostratial ROIs and the aforementioned conditional and parametric event times of interest. All first-level outputs will be moved forward to second-level random effects GLM analyses examining activity and connectivity between groups and correlating demographic variables with brain maps. Analyses will be performed with the hypothesis-driven corticostratial ROIs and a whole-brain mask for exploratory analyses. Voxel-wise statistical thresholds will be set to  $p<0.001$  with contiguous voxel extent thresholds set to 5 and 20 for ROI and whole-brain analyses, respectively. Small volume family-wise error correction for multiple comparisons will be applied.

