### Brain Stimulation and Drug Administration Experimental Sessions (Visits 2-7):

Experimental sessions during Experiments 1 and 2 will last approximately 7 hours and test 6 combinations of TMS and THC on relevant outcome measures (Visits 2-7; Figure 1). Subjects in Experiment 1 will receive real and sham excitatory iTBS of the left DLPFC. Subjects in Experiment 2 will receive real and sham inhibitory cTBS of the left DLPFC. A single bout of iTBS or cTBS (real or sham) TMS will be delivered at a single time point (approximately 3 hours after capsule administration) during each experimental session. Subjects will receive the 6 experimental conditions in random order except that the combination of 30 mg THC + active TMS condition (iTBS or cTBS) will not be administered prior to the administration of 30 mg THC + sham TMS.

Drug Administration: THC (10 and 30 mg) and placebo will be administered orally under double-blind conditions. The oral route was chosen to maintain subject and research staff blindness and to eliminate any expectations that may accompany other routes of drug administration (i.e., smoking). Subjects will ingest capsules with approximately 150 mL of water. Research staff will conduct a mouth check to ensure that the subject swallowed the capsules. Placebo will also be tested and capsules will be filled with a behaviorally inert substance (e.g., corn starch). If heart rate is above 100 bpm before dose administration, the dose will be withheld and heart rate reassessed every 15 minutes for 1 hour. If heart rate has not fallen below 100 bpm after 1 hour, the study physician will be consulted regarding the subject's continued participation in the study.

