Subject monitoring following drug administration during sessions will consist of, at minimum, regularly timed subjective effects questionnaires, cardiovascular assessments, staff observations and spontaneous subject reports.

A field sobriety test (walk and turn, one-leg balance [timed], finger-to-nose and backwards-counting tasks) will be used to assess psychophysical performance when subjects arrive for each session and before they are discharged. Performance on this battery prior to drug administration is designed to ensure the absence of any performance impairment prior to the session and to serve as a pre-drug baseline from which to compare performance on the same battery at the end of the day during discharge assessment. If drug effects are evident at the end of the experimental session, or if subjects report any subjective drug effects, they must remain onsite until these effects dissipate. Previous research indicates that by comparing pre- and post-drug performance on the experimental tasks and the field sobriety test, subtle levels of impairment can be detected.

There are risks associated with leaving the lab following drug administration, if subjects choose to withdraw from a study. Subjects must interact with staff prior to leaving the facility. They will be required to remain in the lab until the staff determines that they are no longer affected by the drug, based on self-report as well as the assessment battery described above; however, they are free to spend their time engaged in activities which are not part of the study. If they choose to leave before the investigators are satisfied that they are no longer affected by the drug, they receive no financial compensation, their study participation is cancelled, they are asked to sign a form that they are leaving against medical advice, and they are required to have someone pick them up at the lab and take responsibility for their safety.

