#### Data Monitoring Plan:

Data from experimental sessions will be collected using a computerized data collection and management system. This system automates the collection of the behavioral and physiological data, which ensures the accuracy and completeness of data collection. The data are stored in a unique file on the hard-drive of the computer and are electronically backed-up at the end of each session. In all instances, the data files do not contain the name of the subject; but instead, each subject is identified by a unique four-digit number. The computer file linking subject names and numbers will be encrypted and only key personnel will have access. Data files for experimental tasks and physiological measures from each experimental session will be managed and combined into a single electronic spreadsheet by automated macros. Data will then be combined into a single electronic spreadsheet and separated by experimental measure for statistical analysis using SPSS (Statistical Package for the Social Sciences, IBM Corp.) software. Neuroimaging data will be stored and backed-up on encrypted and secure servers at the MRISC according to existing and approved UK protocols. Secure copies of structural and functional neuroimaging data sets will be securely routed to the PI's office computer via encrypted network protocols occurring behind the UK firewall. These data will be analyzed using customized Matlab (MATLAB) scripts and an array of neuroimaging software packages, including but not limited to SPM and FSL primary platforms and their associated neuroimaging toolboxes.

The primary outcomes for both experiments are those from neurocognitive tasks measuring decision-making and working memory. Subjective drug effects will also be measured. Changes in outcome variables following active drug and placebo administration will be compared between real and sham transcranial magnetic stimulation (TMS) to determine if excitatory iTBS600 (Exp.1) or inhibitory cTBS600 (Exp. 2) delivered to the left dorsal lateral prefrontal cortex (DLPFC) alters the effects of THC on study outcomes. Data will

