be analyzed using ANOVA with alpha set at 5%. Additionally, functional neuroimaging data from Training Sessions in each experiment will be modeled using traditional mass-univariate approaches (e.g., general linear models and statistical parametric mapping) and newer multivariate pattern analysis (i.e., support vector machine learning) to classify the brain profiles that predict the ability of THC and brain stimulation to impact neurocognitive outcomes.

The quality of manipulated data and data analyses will be monitored by random inspection by the PI and/or other key personnel. Preprocessing and analysis of subject-specific behavior and brain data will begin as individual data are collected. Interim analysis of group data will begin once 25% of the sample is accrued.

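### The pre-drug session baseline has no defined role in the primary ANOVA, and no visit term is stated although real TMS at 30 mg THC always follows sham at 30 mg

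*Combined protocol and SAP*

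**What the plan says.** All references are to the combined protocol and SAP.

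- **Measurement.** Data Collection & Research Materials, under Experimental Session Outcomes: "Performance will be measured on 4 experimental tasks at baseline (approximately 30 minutes after arrival; 1 hour before THC administration". A second measurement follows immediately after TMS, about three hours after the capsules.
- **Method.** The Behavioral Data Analyses paragraph: "Analysis of variance (ANOVA) will be used to compare group demographic data, data from primary outcome measures (above". The Data Monitoring Plan repeats it: "be analyzed using ANOVA with alpha set at 5" percent. Neither place names a covariate, a time factor or a visit term.
- **Comparison.** The Data Monitoring Plan: "Changes in outcome variables following active drug and placebo administration will be compared between real and sham" stimulation. It does not say what the change is measured from.
- **Other pre/post wording.** The section on effects of the study drugs mentions "comparing pre- and post-drug performance on the experimental tasks and the field sobriety test", but for detecting residual impairment at discharge.
- **Mixed models.** These are named only for the reinforcement-learning parameters: "with parameters compared by model comparison and linear mixed modeling".
- **Order.** The six conditions are randomised, except that 30 mg with active TMS "will not be administered prior to the administration of 30 mg THC + sham TMS".
- **Timing.** "Interim analysis of group data will begin once 25% of the sample is accrued". With the 40 subjects given under Data and Safety Monitoring, that is 10 people.

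**The concern.** Each experimental session yields a pair of scores per task, and the plan does not say what is done with the first of each pair. It could be subtracted, used as a covariate, entered as a time factor or ignored. These are different analyses of the primary outcomes (decision-making and working memory), with different precision.

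The order rule raises the stakes. Six repeats of the same tasks can produce practice or fatigue. Full randomisation would balance such a trend across conditions on average, but here the rule places real TMS at 30 mg systematically later than sham at 30 mg. Without a visit term, a trend over visits looks like a stimulation effect at the highest dose, which is the contrast closest to the study's question.

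Group data are to be looked at from 25% accrual, so an open choice could be settled after results have been seen.

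**Working it through.** The documents give no power, SD, correlation or trend, so there is no planned figure to reproduce. r below is the within-person correlation between a session's baseline and its post score, with participant effects removed, because the TMS and dose contrasts are within-person.

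**1. Position of the two 30 mg conditions.** The pair occupies two random places among six, with sham first. The expected minimum is 7/3 = 2.33 and the expected maximum 14/3 = 4.67. The other four conditions average (21 - 7)/4 = 3.5. The expected gap at 30 mg is 4.67 - 2.33 = 2.33 visits.

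**2. Bias in a post-only ANOVA.** For a linear trend of b residual SD per visit, the bias is 2.33b for real minus sham at 30 mg. It is also 2.33b for the 30-minus-0 mg interaction, and 2.33b/3 for the TMS main effect over three doses. At b = 0.15 these are 0.35, 0.35 and 0.117.

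**3. False positives.** Inputs: N = 20 per protocol (40 split evenly, an assumption), two-sided 5%, 19 df. Standard errors in residual SD units are sqrt(2/20) = 0.316, sqrt(4/20) = 0.447 and sqrt(2/60) = 0.183.

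| Test | bias/SE at b = 0.15 | False positives |
|---|---|---|
| Real vs sham at 30 mg | 0.35/0.316 = 1.11 | about 18% |
| 30-minus-0 mg interaction | 0.35/0.447 = 0.78 | about 11% |
| TMS main effect | 0.117/0.183 = 0.64 | about 9% |

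At b = 0.10 the 30 mg contrast has 0.233/0.316 = 0.74, or about 11%. Simulation under the order rule agrees (10-11% and 18% at 30 mg; 8-9% for the main effect at b = 0.15). Change scores at r = 0.3 give about 9% and 14% at 30 mg if only post scores drift, and 5% if baseline and post drift equally. With visit and baseline fitted, the rate is about 5%.

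**4. Precision of the baseline options.** With equal pre and post variance, relative to post-only = 1: change score 2(1 - r); adjusted 1 - r²; ratio of change to adjusted 2/(1 + r).

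| r (assumed) | Change | Adjusted | Change/adjusted |
|---|---|---|---|
| 0.2 | 1.60 | 0.96 | 1.67 |
| 0.5 | 1.00 | 0.75 | 1.33 |
| 0.8 | 0.40 | 0.36 | 1.11 |

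With k = SD of baseline / SD of post, the ratio becomes (k² + 1 - 2rk)/(1 - r²). At r = 0.2 and 0.5 this is 1.09 and 1.00 for k = 0.5, and 2.15 and 1.75 for k = 1.25. Apart from estimating one slope, adjustment is never less precise than subtraction.

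**5. Price of the visit term.** Take total SD 1 and within-person correlation 0.7 (assumed), so residual variance 0.3. The plain post-only SE at 30 mg is sqrt(2 × 0.3/20) = 0.173. A categorical visit term multiplies the variance by about 1.268 within one protocol, or 1.125 if both protocols share it. The SE becomes 0.173 × sqrt(1.268) = 0.195, or 0.173 × sqrt(1.125) = 0.184. Baseline adjustment multiplies the variance by 1 - r², so break-even with the plain ANOVA is r = sqrt(1 - 1/1.268) = 0.46, or sqrt(1 - 1/1.125) = 0.33.

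**The case against.** The strongest reply is that the fix can be less precise than the ANOVA it replaces. That stands: at r = 0.2 its variance at 30 mg is 1.268 × 0.96 = 1.22 times that of plain post-only ANOVA (1.08 times with a shared visit term). Precision alone would not justify the change.

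Second, both trend values are assumed. The training visit familiarises subjects with the tasks, which may flatten any practice trend, and equal drift before and after drug would cancel in a change score. Both points stand. They limit the likely size of the bias, but the order imbalance is fixed by the protocol.

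Four stronger readings are tempting, and the documents do not support them.

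- *The plan subtracts the baseline and so loses a third or more in variance.* Subtraction is one reading. The word *changes* could equally mean THC against placebo, and the pre/post wording elsewhere concerns discharge safety. No r is given, and equal variance is doubtful for VAS items that may sit near zero before drug.
- *The trial's results will carry 18% false positives.* That needs a trend of 0.15 residual SD per visit, and it applies to the 30 mg contrast only.
- *The planned ANOVA ignores person-to-person variation in the TMS effect.* A repeated-measures ANOVA tests real versus sham against that variation. The risk arises only if it is replaced by an intercept-only mixed model.
- *Many participants will be lost from the analysis.* No rate is stated, and a failed alcohol or drug screen leads to a rescheduled visit. Dismissal and withdrawal are foreseen, however, and no rule covers fewer than six sessions.

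**Conclusion.** The gap is real: the baseline is collected, its role is undefined, and no visit term protects the 30 mg contrast from the order rule. It should be fixed, with medium confidence about its size.

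The imbalance of 2.33 visits follows from the protocol alone. The resulting error rates depend on an assumed linear trend and 20 people per protocol. The variance ratios depend on an assumed r and equal pre/post variances. That adjusting is at least as precise as subtracting, apart from the negligible cost of one slope, depends on neither.

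**What to change.** Before any group data are examined, and so before the interim look, state the following for each continuous task outcome.

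- **Response:** the post-TMS score. Say what *changes* means in the Data Monitoring Plan.
- **Fixed effects:** TMS Protocol × TMS Type × THC dose, visit number, and session baseline split into the participant's mean and that session's deviation from it. Say whether the two protocols share the visit term.
- **Model:** a linear mixed model on all available sessions, with a participant effect and a participant-level TMS Type effect. The latter keeps real versus sham tested against person-to-person variation. With an intercept only, main-effect false positives are about 9% or 15% if the SD of that variation is 0.5 or 1.0 residual SD (assumed), against about 5% with the term. If there is no such variation the term is conservative (1.8%).
- **Incomplete participants:** state the missing-at-random assumption, and report the complete-case ANOVA as a sensitivity analysis.
- **VAS items with almost no pre-drug variation:** the baseline terms may be left out if this is stated in advance.

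The order rule is taken as given; nothing here asks for it to change. The cost is some analysis work and the precision loss shown above, with no new data, visits or participants.

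### The PRLC task holds unclaimed rewards, but the learning model as described has no term for this, so fitted c cannot be read as pure perseveration

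*Combined protocol and SAP*

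**What the plan says.** Task 2 in Data Collection & Research Materials is a two-option task with unsignalled reversals and example reward ratios of 6:1, 2:1, 1:2 and 1:6. It states the hold rule, "Once a reinforcer is scheduled for an option, it remains available until that option is chosen", and its consequence: "the longer an option remains un-chosen, the greater the probability that a reinforcer will be delivered by choosing it". A run ends at the first of three limits: a trial count (480 is the example), a time limit (45 minutes is the example), or a reward cap, described as "a maximum number of reinforcers (e.g., 50) associated with one of the two options have been delivered".

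Behavioral Data Analyses, in the same section, describes the model. On the update it says: "The value of the chosen option (option A) is updated via the outcome of the trial according to Equation 1". Delta is the outcome minus an expectation built from that option's own reinforcement history. Choice follows a softmax on the value difference plus a previous-choice term weighted by c, which is defined as "the propensity of the individual to make the same choice on the current trial, regardless of reinforcement history". Alpha, beta and c are fitted by maximum likelihood, fits are compared by AIC and pseudo r-squared, and parameters are compared by model comparison and linear mixed models. On extensions, the text says that "further decision-making complexities (e.g., outcome-specific learning rates or differential future-reward discounting) can be included when warranted". The primary molar PRLC outcome is money earned. Neuroimaging Data Analyses takes alpha, delta and c into the fMRI models.

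**The concern.** The task rewards going back to a neglected option, and the longer the neglect, the better the odds. The model as described holds the un-chosen option's value constant, so it has no value-based reason for that switch. The only remaining term that can absorb systematic switching is c, which moves negative. The plan then interprets c as a tendency unrelated to reinforcement, although on this schedule part of it is a response to reinforcement.

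What is at stake is the reading of c across the six TMS-by-THC sessions. THC is studied here because it impairs working memory and decision-making (Background, Objectives), and keeping track of time since last choice plausibly draws on working memory. If a condition reduces use of the hold rule, fitted c rises without any change in true perseveration. The trial could then report a THC effect on perseveration, or its reversal by TMS, that reflects schedule tracking.

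**Working it through.** The plan gives no figure on this point, so there is none to reproduce.

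**Inputs from the documents:** the hold rule, the example ratios, 480 trials, the 50-reinforcer cap, and the model form (chosen-option update, softmax, previous-choice term, maximum likelihood).

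**Assumed, because the documents do not give them:** summed arming probability per trial (0.3, also 0.5), unsignalled blocks of 70-90 trials, learning rate 0.25, beta 6, and the degree w to which a subject uses the hold rule (0 = none, 1 = full).

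**Step 1: does switching pay?** For an option with arming probability p left for n trials, P(available) = `1-(1-p)^n`. At summed probability 0.3:
- At 6:1, lean p = 0.3/7 = 0.043 and rich p = 0.257. The lean side reaches `1-(1-0.043)^7` = 0.264 at n = 7, above 0.257.
- At 2:1, lean p = 0.10 and rich p = 0.20. The lean side reaches `1-0.9^3` = 0.271 at n = 3, above 0.20.

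Leaving the rich side after a short run is therefore the better-paid choice, while the described model sees no change in the neglected option.

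**Step 2: what does c become?** Simulated choosers used decision value `(1-w)Q + w[1-(1-Q)^n]`, with 40 sessions per row and the 50-reinforcer cap applied. Previous choice was coded +1/-1. The described model was fitted first, then the same model with the hold term.

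| Summed prob. | w | True c | Fitted c, described model (SD) | Fitted c, hold-aware (SD) | Median AIC gain, hold-aware |
|---|---|---|---|---|---|
| 0.3 | 0 | 0 | -0.02 (0.14) | 0.01 (0.15) | -2.0 |
| 0.3 | 0.5 | 0 | -0.40 (0.15) | 0.00 (0.20) | 11.3 |
| 0.3 | 1 | 0 | -0.62 (0.19) | -0.08 (0.18) | 17.4 |
| 0.5 | 0 | 0 | -0.01 (0.20) | 0.04 (0.20) | -1.9 |
| 0.5 | 0.5 | 0 | -0.66 (0.21) | -0.04 (0.29) | 5.5 |
| 0.5 | 1 | 0 | -1.00 (0.29) | -0.08 (0.29) | 12.3 |
| 0.3 | 1 | +0.3 | -0.34 (0.17) | +0.22 (0.17) | 21.6 |

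With equal values, P(repeat) = `1/(1+e^(-c))`. So c = -0.62 means 1/(1+1.859) = 0.35, where the true figure is 0.50. In the last row a perseverating chooser is scored as an alternator.

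**Step 3: sensitivity.**
- Removing the cap (480 trials, w = 1, summed probability 0.3) gives c = -0.59, so the cap neither causes nor removes the bias.
- A second chooser type (beta 4), with a simple choice bonus for time since chosen, gives c = -0.01, -0.30 and -0.52 for no, moderate and stronger bonus.
- Learning rate 0.2 and beta 5 over 480 trials give -0.02, -0.55, -1.05 (rate 0.30) and -0.02, -0.68, -1.16 (rate 0.45) for w = 0, 0.5, 1.
- Other capped runs at rate 0.30 give between -0.53 and -0.94 at full use.
- With no use of the rule, every value lay between -0.12 and -0.01.

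**Step 4: a condition contrast.** At summed probability 0.3, a fall from w = 1 to w = 0.5 with true c unchanged moves fitted c by -0.40 - (-0.62) = +0.22, which exceeds one between-session SD (0.15-0.19).

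**Step 5: delta.** At w = 0, where the described model is correct, mean delta is already +0.20 on switch trials and -0.11 on stay trials, and the chooser's own delta is the same. At w = 1 (summed probability 0.3), fitted against own delta is -0.107 against -0.025 on stay trials and +0.107 against +0.078 on switch trials, with a trial-by-trial correlation of 0.97. For the second chooser type the correlation is 1.00.

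**The case against.** **The flexibility clause covers it.** The plan already compares models by AIC, and its examples of extensions are not exhaustive. That permits a hold-aware model. It does not require one or say what would trigger it, and neither example concerns the hold rule, which is a known feature of the task.

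**Equations 1-3 cannot be seen.** They are in a figures attachment, so a term for the un-chosen option cannot be excluded. This stands. The point applies to the model as the text describes it, and if such a term exists, stating it in the text would largely settle the matter.

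**The size is unstable and conditional.** This also stands. Full-use estimates differ about twofold between sets of assumptions, there is no bias without hold-rule use, and the documents do not show how far subjects use the rule. The direction was the same in every scenario with use.

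**The recovery is close to circular.** The corrective models were fitted to choosers built with the same term, so recovery near zero is a best case. This is a reason to test recovery, and it leaves the bias in the described model untouched.

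**Session-level AIC may be weak.** In one set of capped runs at half use, the AIC advantage was only about 2.7-3.6 points and exceeded 2 in half of runs. Choosing a model session by session could therefore mix models within one subject.

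**A reader might infer that delta maps are confounded with switching.** The documents and the check do not support that. The switch/stay difference in delta is mostly genuine prediction error on this schedule, and the trial-by-trial pattern survives. Scanning takes place only at the Training Session, without THC or theta-burst stimulation, so the fMRI models cannot carry a THC or TMS artefact.

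**Conclusion.** The concern holds for c. The task description says that a neglected option becomes more likely to pay, while the model as described has no term for this and interprets c as independent of reinforcement history. With true c = 0, fitted c runs from about 0 (rule not used) to roughly -0.5 to -1.2 (full use), and the sign can reverse for a chooser with true c = +0.3. These sizes rest on assumed reward rates, block lengths, learner parameters and degree of hold-rule use.

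Three stronger conclusions are tempting and should not be drawn. Delta is little affected (correlation about 0.95 or higher). Money earned does not use c or delta, so the primary molar outcome is untouched. And nothing in the documents shows that THC or TMS does change use of the hold rule; the claim is only that such a change could not be told apart from a change in perseveration. This is a matter for the molecular PRLC analysis.

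**What to change.** In Behavioral Data Analyses:

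1. Pre-specify, as a standard candidate in the AIC comparison, a model with a time-since-last-choice term. One example is decision value `(1-w)Q + w[1-(1-Q)^n]`, where n is trials since the option was last chosen and w is one extra free parameter. An additive time-since-chosen term is an alternative.
2. Report parameter recovery for c under the actual schedule and stopping rule, including choosers not generated from the fitted formula.
3. Choose one model for all subjects and sessions by group-level AIC, so that c is comparable across the six conditions.
4. Report a THC or TMS effect on c as perseveration only if it holds in the hold-aware model; otherwise describe c as a net repeat/switch tendency.
5. State in the text whether Equations 1-3 contain any term for the un-chosen option.

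This uses data already collected and needs one more fit per run. The cost is an extra parameter and a less precise c: the between-session SD was 0.15-0.29 in the table, against 0.14-0.29 for the described model. It was 0.21-0.24 against 0.11-0.13 for the additive version, and could reach about 0.4 in other capped runs. Where the rule is not used, AIC favours the simpler model by about 2 points.
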